5.2 Pre-operative Data Collection

- Patient demographics
- Diagnosis/reason for the primary total knee arthroplasty, operative side
- Preoperative medical history: Relevant concurrent medical condition and treatment
- Knee Society Score (KSS)
- Oxford Knee Score

5.3 Intra-operative Data Collection

- Surgical details
 - Type of anesthesia
 - Anesthesia class ASA
 - Systemic prophylactic therapy
 - Surgical approach
 - Surgeon initials
 - Skin to skin and tourniquet time
 - Blood loss
- Simplex HV details
 - Cement storing temperature
 - Operating room temperature
 - Cement type

- Cement use
- Cement preparation
- Triathlon Total Knee Replacement details
 - Femoral component
 - Tibial component
- Intra-operative Adverse event or device deficiency

5.4 Post-operative Data Collection

Data collection at 24 months (+ 2 months) postoperatively and optional at 5 years postoperative.

- Knee Society Score (KSS)
- Oxford Knee Score (OKS)
- X-ray collection for independent analysis
 - A/P view
 - Lateral view
- Elective surgery since study surgery
- Post-operative Adverse event or device deficiency

6 Adverse Events

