Evaluation	Pre-operative	Intra-operative	24 (+2) months post-operative	27 months up to 5 years post-operative
Inclusion/Exclusion	x			
Demographics & Medical History	x			
KSS	x		x	optional
Surgical Details		x		
Implant and Cement Details		x		
OKS	x		x	optional
A/P and Lateral X-ray Interface			x	optional
Adverse Events		x	x	per protocol

Table 1 Evaluation Schedule

1 Introduction

This document is a protocol for a retrospective human research study. This study will be conducted in compliance with the protocol, international standard ISO 14155 Standards, associated Federal regulations and all applicable research requirements.

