5.1 Inclusion/Exclusion Criteria

Inclusion Criteria:

- A. The Patient is age 18 or over at time of study device implantation
- B. Patients who have undergone primary Triathlon Total Knee Arthroplasty in which Simplex HV/Simplex HV Gentamicin was indicated for fixation and used on label
- C. Patients who have been followed for at least 24 months postoperatively

Exclusion Criteria:

- A. Patients who have undergone revision surgery
- B. Patients who have undergone bilateral Knee Arthroplasty
- C. Patients contraindicated for either the devices implanted, or the cement used, according to medical history review and instructions for use
- D. Patient has a cementless tibial baseplate.
- E. Patient has an active or suspected latent infection in or about the affected knee joint
- F. Patient has muscle loss or neuromuscular impairment in the affected limb that would create an unjustifiable risk
- G. Patient is immunologically suppressed or receiving steroids in excess of normal physiological requirements (e.g. > 30 days)
- H. Patient has a known hypersensitivity to any of the cements constituents or in patients with severe renal failure
- I. Patient is a prisoner

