7.1 Definition of Aseptic Loosening

X-rays will be collected at least at two years after surgery for independent analysis of radiolucency occurrence at implant-cement interface by an independent reviewer

[figure not shown]
- Radiolucency at implant-cement interface
 - Tibia A/P
 - Tibia lateral
 - Femur PS lateral or Femur CR lateral

Radiolucencies at the implant-cement interface more than 2 mm in all zones of a component is defined as aseptic loosening.

[figure not shown]
Zones Tibia A/P⁷

Zones Tibia Lateral⁷

Zones Femur PS Lateral⁷

Zones Femur CR Lateral⁷

[figure not shown]

Figure 2 Component zones

8 Data Management

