9.3 Missing Data

No missing data will be imputed

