 Gastrointestinal tract/metabolism			 No treatment			 Treatment						
 Blood and blood forming organs			 No treatment			 Treatment						
 Cardiovascular system			 No treatment			 Treatment						
 Skin			 No treatment			 Treatment						
 Reproductive system			 No treatment			 Treatment						
 Endocrine system			 No treatment			 Treatment						
 Infections and Infestations			 No treatment			 Treatment						
 Malignant/Immune disease			 No treatment			 Treatment						
 Muscles, bones and joints			 No treatment			 Treatment						
 Brain and nervous system			 No treatment			 Treatment						
 Respiratory system			 No treatment			 Treatment						
 Other			 No treatment			 Treatment						
 Other			 No treatment			 Treatment						
Investigator Name (Print)						For Stryker Use Only			INITIAL/DATE:			
						Stamp Date Received:			Monitored:	/		
									Receipt:	/		
									Entry:	/		
									Verification:	/		
Investigator Signature												
Date												
									D D	M M M	Y Y Y Y	

Stryker® Simplex HV Retrospective Study			
Page 1 of 1	Knee Society Score	Patient ID 8 0	
		Study#	Center#
		Subject#	Side (L/R)
GENERAL INFORMATION			
Patient code (Use AA, BB,...AB)		Date of examination 	
Pre-op visit 	Follow-up at  12-24 months (+2 months) post study surgery  5 years (± 3 months) post study surgery, specify  years  months		

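### The two-year window for KSS, OKS and films is stated inconsistently, and its narrow form suits a retrospective study poorly

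*Combined protocol and SAP*

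**What the plan says.** - **Section 5.4:** "Data collection at 24 months (+ 2 months) postoperatively and optional at 5 years postoperative". There is no tolerance before 24 months.
- **Table 1:** KSS, OKS and the X-ray are required in the column "24 (+2) months post-operative" and optional in the next, "27 months up to 5 years post-operative".
- **Appendix B, KSS, OKS and Follow-up forms:** the two-year box reads "12-24 months (+2 months) post study surgery" and the late box "5 years (± 3 months) post study surgery, specify".
- **Section 7.1:** "X-rays will be collected at least at two years after surgery", with no upper limit.
- **Section 5.1, Inclusion C:** "Patients who have been followed for at least 24 months postoperatively", so follow-up is open-ended upwards.
- **Section 4.1:** the data come from existing records of routine care.
- **Section 9.3:** "No missing data will be imputed".
- **Section 9.4.3:** retrospective data up to five years are to be analysed. No section says which time point a score at, say, 28 months belongs to, or which visit counts when a knee has several.

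**The concern.** In a prospective study a visit window steers scheduling. Here every visit has already taken place, so the window can only decide which existing records count as two-year data. The protocol body and the forms give abstractors different answers to that question.

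Under the protocol body, an eligible knee first seen at 28 months has no required two-year score or film. Under the forms, a visit at 12 months can be ticked in the two-year box, and a visit at 28 months has no box.

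At stake are the OKS and KSS results, which are part of the secondary objective, and the independent radiolucency read. Section 2.3 allows a site to enrol only one cement type, so differences between sites in recall habits could make score availability differ by cement.

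**Working it through.** **Step 1. The windows side by side (months after surgery).**

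| Source | Two-year window | Late window | Unassigned |
|---|---|---|---|
| 5.4 and Table 1 | 24 to 24 + 2 = 26 | 27 to 60, optional | 26 to 27 (continuous time) |
| KSS, OKS, Follow-up forms | 12 to 24 + 2 = 26 | 60 − 3 = 57 to 60 + 3 = 63 | 26 to 57 |
| 7.1 (films) | from 24, no upper limit | none stated | none |

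The two-year windows differ at the lower limit (24 or 12) and, for films, at the upper limit (26 or none). The late windows differ at both ends. A 28-month visit is optional in Table 1, has no box on the forms, and gives an acceptable film under 7.1.

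**Step 2. How many visits the narrow window could miss.** The plan gives no figure to reproduce: there is no visit-time distribution and no expected number of in-window scores. Assume that routine two-year visit times T are normal with mean 24 months. Inclusion C requires at least 24 months of follow-up, so the relevant share is among visits at or after 24 months. Half of the distribution lies there, so

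P(24 ≤ T ≤ b | T ≥ 24) = 2Φ((b − 24)/SD) − 1.

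- SD 1.5, b = 26: 2Φ(1.333) − 1 = 0.818
- SD 3, b = 26: 2Φ(0.667) − 1 = 0.495
- SD 1.5, b = 30: 2Φ(4) − 1 > 0.999
- SD 3, b = 30: 2Φ(2) − 1 = 0.954

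| SD (months) | 24–26 | 26–27 | 27 or later | 24–30 |
|---|---|---|---|---|
| 1 | 95% | 4% | 0.3% | >99% |
| 1.5 | 82% | 14% | 5% | >99% |
| 2 | 68% | 18% | 13% | >99% |
| 3 | 50% | 19% | 32% | 95% |
| 4 | 38% | 16% | 45% | 87% |

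With mean 25 instead of 24, 24–26 captures 81% (SD 1) down to 33% (SD 4). At mean 25 and SD 4, 24–30 captures (Φ(1.25) − Φ(−0.25))/(1 − Φ(−0.25)) = 0.493/0.599 = 82%.

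**Step 3. Scale.** If each of the 100 knees per cement type had one such visit, about 82 (SD 1.5) or 50 (SD 3) would have an in-window score.

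**Step 4. If the forms govern instead.** With mean 24, the 12-to-26-month box takes in 91% (SD 1.5) or 75% (SD 3) of all two-year visits. In both cases 50 of those percentage points are visits before 24 months. Annual visits near 12 months would also fit the box, and no rule chooses between them and the later visit.

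**The case against.** The strongest reply is that nothing is actually thrown away. No section tells anyone to delete an out-of-window score. Table 1 has a column for later data, 9.4.3 analyses data up to five years, 7.1 sets no upper limit for films, and 8.5 does not list visit timing among its examples of major deviations. This stands: what is missing is an assignment rule, and a loss of two-year data follows only if the stated windows are applied literally.

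The 26-to-27-month hole depends on reading the labels as continuous time. If Table 1 counts completed months, 26 runs straight into 27, and capture in Step 2 rises to 1 − 0.046 = 95% (SD 1.5) or 1 − 0.317 = 68% (SD 3). This also stands as an ambiguity. It does not cure the form boxes, which would still leave 27 to 57 months uncovered.

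The late box on the KSS and OKS forms has fields for years and months, so a 28-month visit could be written in. It would then sit under a label of five years ± 3 months.

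The visit distribution is assumed. With tight recall (SD 1) the loss is about 5%, so a large loss is possible but not shown.

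Finally, KSS and OKS are descriptive, with no test or threshold. That limits the consequence without removing it.

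**Conclusion.** The inconsistency between Table 1 and 5.4, 7.1 and the forms is a matter of text and needs no assumption. The amount of two-year data left out does rest on one. With visits normal around 24 months, the 24-to-26-month window captures about 82% (SD 1.5) to 50% (SD 3) of visits at or after 24 months, and over 95% are captured by 24 to 30 months. Across all the values tried, capture for 24 to 26 months runs from 95% down to 33%.

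Three stronger readings are tempting and not supported:

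- **That the plan discards out-of-window data.** No section says so.
- **That a visit at 23.5 months is unusable.** That follows from Table 1 and 5.4, but such a visit fits the two-year box on the forms.
- **That the primary result is at risk.** Success is absence of revision for aseptic loosening at 24 months, estimated by Kaplan-Meier, and needs no score or film from a windowed visit.

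The point should be corrected, but it concerns the secondary scores and the radiolucency read only.

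**What to change.** 1. State one gap-free two-year window in Table 1, 5.4, 7.1 and the form boxes, for example the first KSS, OKS and film from 24 to 30 months. A lower limit of 24 months matches Inclusion C. The upper limit of 30 is a proposal and is not derived from the documents.
2. Start the late column directly after that window, and give Table 1 and the forms the same late limits.
3. Remove the 12-month lower limit from the two-year box.
4. Assign visits by the examination and X-ray dates already on the forms, not by the ticked box.
5. Report, by cement type, the number of knees with an in-window score and film.
6. Show the 24-to-26-month subset as a sensitivity summary.
7. Keep the revision endpoint fixed at 24 months by date.

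The cost is wording in the protocol and forms. The downside is a slightly wider spread of assessment times, which the recorded dates allow the report to show.

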6.1 Reporting of Adverse Events

The AE reporting requirements for this study are as follows:

- All AEs that meet the definition of serious
- All AEs related to the operative site, regardless of seriousness or time of occurrence

On retrospective review of postoperative data, investigators and study coordinators (SCs) will search the subject's hospital files as to whether they have seen a doctor for any reason, been hospitalized for any reason or have a current impediment to their function.

If it is determined upon this further investigation that a protocol-defined AE has occurred, the SC will be responsible to complete an AE CRF. If the event is related or uncertain related to the Triathlon TKA or to Simplex HV, the investigator will verify if the event has been reported to Stryker at time point of occurrence or will report at time point of data review at the latest. The event shall be reported to Stryker and to the IRB/EC, as required.

The following decision tree facilitates identification of AEs for which reporting is required under this study protocol:

[figure not shown]
Figure 1. Adverse Event Decision Tree

Figure 1 Adverse event decision tree

General Retrospective Review Findings

At screening for inclusion into the study, any clinically significant abnormality should be recorded as a preexisting condition and reported on the Demographics CRF. From the time of surgery forward, any new clinically significant findings or abnormalities that meet the definition of a protocol defined AE must also be recorded and documented as an AE until the end of the observation period or maximum at the five years follow-up.

Adverse Event Reporting Period

The study period during which AEs must be reported is defined as the period from the surgery to the last protocol specified follow-up.

During retrospective review of the subject's hospital files, information on protocol defined AEs shall be recorded in the AE CRF. The clinical course of each event should be followed until resolution or until it is determined at the end of the study that the AE will not resolve.

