4.2 Patient Informed Consent and Guidelines

The study protocol will be submitted for IRB/ EC Review. As pseudonymized retrospective patient data will be used, a requirement for informed consent is not expected, however waiver of consent from the IRB/EC is required.

5 Study Details

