9.1 Study Objectives

9.1.1 Objective Analysis

To evaluate the success rate of cemented Triathlon Total Knee components implanted using Simplex high viscosity bone cement (Simplex HV). Success is defined as absence of revision of cemented Triathlon Total Knee components implanted with Simplex HV for aseptic loosening at two years postoperative. 95% confidence interval of the success rate will be presented as well.

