9.4 Statistical Methodology

9.4.1 Data Summary

Descriptive statistics will be computed for all baseline conditions and demographic parameters. That is, for continuous data, the N, mean, median, standard deviation, minimum and maximum will be computed. For categorical data, the frequency will be computed. The data will be presented by appropriate subgroups (e.g., center, gender).

A Kaplan-Meier survivorship curve will be displayed for revision and/or removal of the Triathlon total knee arthroplasty cemented with Simplex HV for aseptic loosening.

A Kaplan-Meier survivorship curve will be displayed for all-cause revision and/or removal of the Triathlon total knee arthroplasty cemented with Simplex HV with Gentamicin for aseptic loosening.

Two year Kaplan-Meier success rate with 95% CI will be presented.

For all additional data collected that are not required for direct support of a study objective, data will be summarized according to follow-up. For parameters represented by continuous variables (e.g., ROM), the summaries will consist of the N, mean, median, standard deviation, minimum, and maximum values.

Documentation of statistical analyses utilizing SAS® software version 9.3 or higher will be maintained.

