9.4.2 Sample Size Justification

No sample size calculation because a number of 100 cases per study arm was pre-defined by the regulatory body.

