Date	 D D /  M M M /  Y Y Y Y						Receipt:	/
							Entry:	/
							Verification:	/

Stryker® Simplex HV Retrospective Study										
Page 1 of 1	Follow-up			Patient ID						
				8 0						
				Study#	Contor#	Subject#	Side (L/R)			
GENERAL INFORMATION										
Patient code (Use AA, BB,...AB)	Date of examination									
	D	D	M	M	M	Y	Y	Y	Y	
	Follow-up at:			 12-24 months (+2 months) post study surgery  5 years (\pm 3 months) post study surgery, specify						
4. X-RAY COLLECTION (A/P and lateral view)										
Date of x-ray				 x-ray not available						
	D	D	M	M	M	Y	Y	Y	Y	

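### No evidence standard for an unrevised knee at 24 months: a knee last examined earlier, or revised for loosening elsewhere afterwards, can count as a primary success

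*Combined protocol and SAP*

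**What the plan says.** **Source of the data.** Section 4.1 draws everything from the centre's charts, images and routine-care follow-up. For post-operative events, section 6.1 says that investigators and coordinators "will search the subject's hospital files". Section 4.2 expects no individual consent and notes that "waiver of consent from the IRB/EC is required". No patient contact, registry linkage or enquiry at other hospitals is described.

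**Endpoint and analysis.** Section 9.1.1 states: "Success is defined as absence of revision of cemented Triathlon Total Knee components implanted with Simplex HV for aseptic loosening at two years postoperative", and adds: "95% confidence interval of the success rate will be presented as well". Section 9.4.1 says: "Two year Kaplan-Meier success rate with 95% CI will be presented". The interval method, the censoring date and the evidence needed for an unrevised knee are not stated. On numbers, section 9.4.2 says: "No sample size calculation because a number of 100 cases per study arm was pre-defined by the regulatory body". Section 9.4.4 limits the analysis to non-censored subjects who are available for it, and defines neither term.

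**Follow-up.** Inclusion C asks for at least 24 months of follow-up. Section 5.4 and Table 1 set the visit at 24 months plus two, and section 7.1 plans films at two years or later for radiolucency review. In Appendix B, however, the KSS, OKS and Follow-up forms label the same visit as 12 to 24 months plus two. The film item on the Follow-up form can be closed with "x-ray not available". Its event item offers No, Yes for aseptic loosening, or Yes for another reason. Another item asks about surgery on the other knee and both hips. No item asks whether the study components are still in place.

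**The concern.** The primary result is a proportion close to 100% with a confidence interval, so a handful of knees decides it. Success is the absence of a record, and the forms do not separate a knee confirmed in place at 24 months from one about which the chart is silent. If the last knee visit was at month 12, or if a loosening revision was done at another hospital after that visit and never reached the chart, the natural entry is No and the knee joins the successes. The opposite error, a recorded loosening revision that never happened, has no comparable route. The mistakes therefore favour the device, and the reader of the report cannot see how many knees are affected.

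**Working it through.** The plan states no expected rate, margin or calculated sample size, so it has no figure to reproduce. The steps below trace how status reaches the endpoint and then size the effect.

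**1. Visit windows side by side.** Section 5.4 and Table 1 allow months 24 to 26. The three forms allow months 12 to 26. A form completed at month 12 leaves 24 − 12 = 12 months of the endpoint period unobserved, yet fills the slot for the primary assessment.

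**2. Can Kaplan-Meier repair this?** The estimate is S(24) = ∏(1 − d/n at risk). It handles early last contact only if such knees are censored at that contact. If only non-censored subjects enter, every n at risk is reduced by events alone and S(24) collapses to (n − d)/n, the simple proportion. Illustration with 100 knees, one revision seen at 18 months, and m knees last seen at 12 months:
- carried as successes: 1 − 1/100 = 99.0%
- censored at 12 months: 1 − 1/(100 − m) = 98.9% (m = 10), 98.75% (m = 20), 98.6% (m = 30)

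**3. Effect of one missed loosening revision.** The exact (Clopper-Pearson) 95% interval is my choice, as the plan names none. With zero failures the lower bound is 0.025^(1/n).
- 99/100: 99.0%, lower bound 94.6%
- 100/100: 100%, lower bound 0.025^(1/100) = 96.4%

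The rate rises by 1.0 point and the lower bound by 96.4 − 94.6 = 1.8 points. This assumes that a detected revision is counted as a failure. If Exclusion A, on patients who have had revision surgery, were read to remove the knee, detection would give 99/99 with lower bound 0.025^(1/99) = 96.3%, and missing the revision would change almost nothing.

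**4. Chance of at least one miss per 100 knees.** P = 1 − (1 − p·f)^100, where p is the true 24-month rate of revision for aseptic loosening and f the share of those revisions that goes unrecorded. The documents give no f; 5% to 25% is an assumption. The only event figure in the documents is one loosening revision in 1851 knees (section 1.1), from a different cohort of obese patients.

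| p | f | P |
|---|---|---|
| 1/1851 | 5% | 0.3% |
| 1/1851 | 25% | 1.3% |
| 1% (assumed) | 5% | 4.9% |
| 2% (assumed) | 10% | 18.1% |
| 4% (assumed) | 25% | 63.4% |

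**5. Effect of requiring evidence.** Take 100 knees, no revision seen and 10 unconfirmed. Dropping the 10 gives 90/90, lower bound 0.025^(1/90) = 96.0%, against 96.4% for 100/100. Counting all 10 as failures gives 90/100 = 90% (82.4–95.1%).

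**The case against.** The strongest reply is that the protocol already requires what is missing. Inclusion C must be ticked Yes before enrolment, and enrolling an ineligible patient is a listed major deviation (section 8.5). Knee scores and films are scheduled at 24 months, the Follow-up form carries an examination date and an investigator signature, and monitors check forms against source. A patient actually examined and filmed at the centre at 24 months would normally reveal an earlier revision. This largely stands where the visit takes place as section 5.4 intends. It does not cover a visit at month 12, which the forms accept, or an absent film, and monitoring cannot find an event that the source lacks.

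Four stronger readings are tempting, and the documents do not support them.
- *Every missed revision inflates the rate.* Only revision for aseptic loosening is a failure. A missed revision for infection, which section 1.1 ranks as the commonest cause of failure, leaves the failure count unchanged.
- *A revision elsewhere leaves no trace.* The section 6.1 search covers any doctor seen and any hospital stay, so an outside letter or later film may well be on file.
- *The plan imputes success despite section 9.3.* No passage scores a silent chart as unrevised. The effect comes from the form's answer options and undefined terms.
- *A miss is likely.* The upper end of the range rests on assumed inputs; at the only rate in the documents a miss is rare.

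**Conclusion.** The point holds as a gap in endpoint ascertainment on the primary outcome, worth closing but not shown to be large. As written, the forms and section 9.4.4 allow a knee of unknown 24-month status to enter as a success, and the planned Kaplan-Meier estimate cannot be relied on to prevent it. For loosening revisions the direction is certain: upward or none. The size is unknown. Per arm of 100 it is 1.0 point on the rate and 1.8 points on the lower bound for each first miss, conditional on Exclusion A not removing a detected revision. The probability of any miss runs from 0.3–1.3% at 1/1851 to 5–63% at 1–4%, all with an assumed 5–25% unrecorded. The argument about knees not examined at 24 months rests on the clash between form and protocol windows and on an undefined notion of being followed, not on any explicit permission.

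**What to change.** 1. Add to the Follow-up CRF: *original components in situ: yes / no / not documented*, with date and source.
2. State in sections 9.1.1 and 9.4.1 that a knee is event-free at 24 months only if a dated knee examination, film or knee-related note at 24 months or later documents it; otherwise it is censored at the last such contact.
3. Remove non-censored from section 9.4.4 so that censored knees stay in the Kaplan-Meier analysis, and reconcile the visit window on the KSS, OKS and Follow-up forms with section 5.4.
4. Report the number of unconfirmed knees by centre and cement. Show the result with all of them as failures only as a labelled worst-case bound.

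The cost is one form item and a few sentences. The information comes from existing charts, needs no patient contact and leaves the consent waiver untouched. If Inclusion C works as intended, few knees will be affected and the table will show that. The downsides are a slightly wider interval (96.0% against 96.4% in the illustration) and a worst-case bound that can look poor (90%, 82.4–95.1%, with 10 of 100 unconfirmed), which is why it should not be read as an estimate.
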